# 8.1.5 Early Treatment Termination (Parts A and B)

Subjects who discontinue study drug will be asked to return to the clinical site for a Safety Follow-up Visit at 28 days after their last dose of study drug. As applicable, subjects who discontinue study drug will be asked to complete all follow-up assessment outlined in Section 8.1.4 as applicable.

#### 8.1.6 Definition of End of Study

Study completion is defined as the time when study drug administration is permanently discontinued due to any reason and the Safety Follow-up Visit or radiologic follow-up (when applicable) after the last dose of study drug has been completed.

The final analysis of study data may be performed when the last subject treated completes at least 6 cycles of treatment or discontinues the study. The additional data for any subjects continuing to receive study treatment after the data cutoff date for the primary clinical study report (CSR) will be further summarized in a report upon completion of the study when all subjects have discontinued study treatment and all required follow-up has been completed or the subject has died, been lost to follow-up, or withdrawn consent to further participation in the study.

## 8.2 Rationale for Study Design and Study Drug Regimens

# 8.2.1 Rationale for Study Design

The primary objectives of Part A of the study are to evaluate safety and determine the MTD of VX-984 in combination with PLD in subjects with advanced solid tumors. Three subjects will be enrolled at the starting dose of VX-984 and PLD. In order to limit subjects being treated at a non-efficacious dose, the initial dose escalation will allow for 100% escalation

[figure not shown]
until 1 subject has a treatment-related or possibly-related DLT or toxicity of CTCAE Grade 3 or worse; or 2 subjects (who may be in different cohorts) have a toxicity of CTCAE Grade 2.

Upon occurrence of a DLT, dose escalation will be guided by BLRM with EWOC principle similar to that proposed by Babb et al. The use of BLRMs for Phase I studies has been advocated by the European Medicines Agency (EMEA) guideline on small populations (2006) and by Rogatko et al.

Subjects enrolled in Part A will have any advanced solid tumor that has failed treatment with at least 1 line of therapy, and have no standard or approved therapy available for treatment of their disease or would potentially be candidates for treatment with PLD. In general, response rates of many advanced solid tumors to second- and third-line therapies are limited. Thus, there is a potential for this population to benefit from the addition of a potential chemotherapy-enhancing agent.

The primary objectives of Part B are to evaluate the safety, tolerability, and OR of VX-984 in combination with PLD in subjects with previously-treated endometrial cancer. There is no approved or standard treatment for advanced recurrent endometrial cancer following a platinum based first-line regimen, and PLD is frequently used as second-line treatment. In xenograft models using cancer cell lines or primary patient tumors, doses of VX-984 combined with PLD significantly enhanced the anti-cancer activity of PLD when VX-984 was administered 16 hours after PLD, and was generally well-tolerated. The trigger for the initiation of the expansion cohort will be achieving a tolerated dose of PLD at or near SOC doses in combination with PLD at doses above the predicted efficacious dose in Part A.

# 8.2.2 Rationale for Study Drug Starting Dose and Duration

The approved single-agent dose of DOXIL®/CAELYX® is 50 mg/m² for ovarian cancer.  To reduce the potential of increased toxicities of PLD when dosed in combination with VX-984, PLD will be administered at 40 mg/m², which is frequently used in the clinic.

The dosing schedule for VX-984 is based on optimal timing of DNA-PK inhibition in relation to DNA-damaging drug exposure. Nonclinical data supports administration of VX-984 for 3 days starting 12 to 24 hours after the initial PLD dose. This schedule will minimize the potential for toxicity and is expected to cover time of the maximum concentration ( $t_{max}$ ) and at least one terminal phase half-life ( $t_{1/2}$ ) of PLD in tumors. 

# 8.2.3 Rationale for Study Assessments

Subjects will be monitored frequently for AEs that may be of potential consequences, based on nonclinical toxicology of VX-984 or based on prior experience in patients treated with PLD, using labs, ECGs, and echocardiograms.

CT scans will be used periodically to monitor tumor response to treatment, and response will be judged using RECIST 1.1. Subjects who do not demonstrate response to therapy will discontinue treatment.

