## 7.2.2 Secondary Endpoints

- PFS
- RD as evaluated by CT scan and quantified by RECIST 1.1
- OS
- Clinical benefit (CR + PR + SD of at least 4 months)
- Plasma PK parameter estimates of VX-984 when administered in combination with PLD, derived from plasma concentration-time data.

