## 8.1.2.1.4 Treatment Duration and Disease Assessments

At all dose levels of VX-984, subjects will complete a total of up to six 28-day cycles of VX-984 and PLD combination therapy. Subjects with tumors responding to treatment may continue treatment past 6 cycles with the agreement of the Investigator and medical monitor until disease progression, unacceptable toxicity, withdrawal of consent, or until exposure to PLD exceeds 550 mg/m^2. Staging CT scans will be performed at the end of every 2 cycles (see Table 3-3). If there is evidence of progressive disease as determined using RECIST 1.1, the subject's treatment will be discontinued. In addition, transthoracic echocardiograms will be performed at baseline and at the end of every 2 cycles (see Table 3-3). After 6 cycles, CT scans will be performed at the end of every 2 to 3 cycles (see Table 3-3).

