## 8.1.2.2 Part B

During each cycle, subjects will be administered PLD on Day 1, and VX-984 will be dosed on Days 2 to 4 of a 28-day cycle unless in Part A the number of days was decreased due to tolerability. Treatment Period assessments are listed in Table 3-3. Approximately 40 subjects will receive VX-984 with PLD at the MTD or lower, as determined during the dose escalation phase.

Upon completion of the first cycle of treatment for at least 10 subjects within Part B, if the observed DLT rate exceeds 33.3%, the BLRM will be re-run to confirm that the estimated MTD still satisfies the overdose criteria of the model. If the dose fails to satisfy the criteria, a

change to the dose under study may be made according to the BLRM recommendation after review of the clinical data.

Subjects will continue to receive treatment until disease progression, unacceptable toxicities, or withdrawal of consent. Subjects will be evaluated by CT scans at the end of every 2 cycles for the first 6 cycles and every 2 to 3 cycles thereafter (see Table 3-3). If in the opinion of the Investigators, subjects may benefit with continued treatment with PLD and VX-984, subjects may continue to receive treatment beyond the total exposure of 550 mg/m² PLD. If there is evidence of progressive disease as determined using RECIST 1.1, treatment will be discontinued. In addition, subjects will be evaluated by transthoracic echocardiogram at baseline and at the end of every 2 cycles (see Table 3-3).

All subjects who meet the eligibility criteria and are administered at least 1 dose of VX-984 will be evaluable for safety. Subjects who meet the eligibility criteria, are administered at least 1 cycle of study drug, and have a baseline scan will be evaluated for efficacy. For subjects requiring palliative radiotherapy, irradiated lesions will be evaluable for progression, not response.

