#### Part B:

For drug-related toxicity, the following modifications of drug dose and schedule will be made:

- In case of non-hematologic Grade 3 or higher toxicity (excluding fatigue or nausea/vomiting/diarrhea adequately managed by supportive care), treatment will be interrupted and may be resumed when all toxicities have returned to Grade < 2, at the discretion of the Investigator
- For the following hematologic toxicities, once the toxicity has returned to Grade < 2, dosing can be resumed with a 25% reduction in VX-984 dose. If, after 25% reduction of

VX-984 dose, any of the below drug-related hematologic toxicities are subsequently observed, then, the dose of PLD will be reduced by 25%

- o Grade 4 thrombocytopenia
- Febrile neutropenia (growth factor support, per site protocol, may be used in lieu of dose reduction)
- o Grade 4 neutropenia lasting more than 7 days (growth factor support, per site protocol, may be used in lieu of dose reduction)
- For the following non-hematologic toxicities, once the toxicity has returned to Grade < 2, dosing can be resumed at a lower dose of chemotherapy. PLD dose will be reduced by 25%. If any of the below drug-related toxicity is subsequently observed with the reduced dose of chemotherapy, VX-984 dose will be reduced by 25%
  - o Grade 3 non-hematologic toxicity (Except for fatigue or nausea, vomiting, or diarrhea adequately controlled by medication)
  - o Any non-hematologic toxicity requiring dose delay of more than 2 weeks.
- For Grade 4 non-hematologic toxicity, treatment will be interrupted and may be resumed at a lower dose when toxicity has returned to Grade < 2 or subjects may be removed from the study. VX-984 dose will be reduced by 25%. In addition, the PLD dose will be reduced by 25%
- For HFS and stomatitis, modify PLD doses according to DOXIL package insert
  - For Grade 1 HFS and stomatitis: if no previous Grade 3 or 4 HFS, no dose adjustment. If previous Grade 3 or 4 HFS, delay dose for up to 2 weeks, then decrease PLD dose by 25%
  - o Grades 2, 3 and 4 HFS and stomatitis: delay dosing up to 2 weeks or until resolved to Grade 0 or 1, then decrease PLD dose by 25%. Discontinue treatment if no resolution after 2 weeks

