# 10.6 Missed Doses and Study Visits

Treatment will be interrupted because of Grade 3 or higher toxicity during any cycle beyond Cycle 1. Treatment may be resumed as described in Section 10.5.

Study visits that are missed because of clinic or subject unavailability (e.g., for reasons of public holiday, clinic closure, urgent personal matter, transportation problems), should be

made up when and if reasonably possible. For delayed doses, the dosing schedule should continue from the date of the delayed dose without omitting any doses of chemotherapy or any rest intervals between chemotherapy, if possible. Whenever possible, subsequent doses of chemotherapy should be advanced in time to synchronize with the actual date of administration of the delayed dose.

The relative timings of all other assessments and drug dosing may be moved to accommodate subject and clinic availability. Delays between sequential cycles in therapy, other than for reasons of toxicity, should not exceed 7 days, except as approved by the Sponsor medical monitor.

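### Protocol Sections 8.2.3 and 10.6 word stopping and interruption more broadly than the operative sections, so some subjects fall under two different rules

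*Protocol*

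**What the plan says.** **Stopping.** Section 8.2.3 first says that response is judged on CT by RECIST 1.1, then adds: "Subjects who do not demonstrate response to therapy will discontinue treatment". It names no study part, scan or cycle.

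The operative sections use another trigger:
- Part A (8.1.2.1.4): "At all dose levels of VX-984, subjects will complete a total of up to six 28-day cycles of VX-984 and PLD combination therapy", and "If there is evidence of progressive disease as determined using RECIST 1.1, the subject's treatment will be discontinued". Beyond six cycles, only subjects whose tumors are responding may continue.
- Part B (8.1.2.2): "Subjects will continue to receive treatment until disease progression, unacceptable toxicities, or withdrawal of consent".
- Stopping rules for both parts (8.1.3): progression after Cycle 1 ends treatment. Stable disease is not listed.
- Efficacy text in Section 11: stopping or extending therapy follows the local reading of progression on CT.

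Sections 9.5 and 10.7 both refer to 8.1.3 for stopping.

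**Interruption.** Section 10.6 says: "Treatment will be interrupted because of Grade 3 or higher toxicity during any cycle beyond Cycle 1". It refers to 10.5 for resumption. Section 10.5 is narrower. The Part B rule for non-hematologic Grade 3 or higher toxicity carries an exception: "excluding fatigue or nausea/vomiting/diarrhea adequately managed by supportive care), treatment will be interrupted". The Part A rule for neutropenia or thrombocytopenia names a delay at Grade 4 only.

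**The concern.** Both general sentences are mandatory and unqualified, and neither matches the sections that tell a site what to do. A site that follows 8.2.3 takes a stable subject off treatment; a site that follows 8.1.2.1.4 or 8.1.2.2 keeps that subject on. A Part B site that follows 10.6 holds dosing for a toxicity that 10.5 exempts.

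Whether a subject stays on treatment is a patient-care matter first. For the analysis, number of cycles, treatment duration, cumulative dose and the chance of a later response would depend partly on which sentence a site followed.

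**Working it through.** The plan states no figure on this point, so the check sets the texts side by side.

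**1. Is stable disease a non-response?** Yes. Section 8.2.3 ties response to RECIST 1.1, and SAP Section 14.1 counts only CR or PR in the ORR.

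**2. Where the texts differ**

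| Situation | General sentence | Specific rule | Agree? |
|---|---|---|---|
| Part A, stable disease, Cycles 1 to 6 | 8.2.3: stop | 8.1.2.1.4: up to six cycles, stop on progression | No |
| Part A, stable disease, after Cycle 6 | 8.2.3: stop | 8.1.2.1.4: only responders continue | Yes |
| Part B, stable disease, any cycle | 8.2.3: stop | 8.1.2.2: continue to progression, toxicity or withdrawal | No |
| Part B, after Cycle 1, Grade 3 or higher fatigue, or managed nausea, vomiting or diarrhea | 10.6: interrupt | 10.5 Part B: exempt | No |
| Part A, after Cycle 1, other Grade 3 non-hematologic toxicity | 10.6: interrupt | 10.5 Part A: hold dosing, no exemption | Yes |
| Part A, after Cycle 1, Grade 3 neutropenia or thrombocytopenia | 10.6: interrupt | 10.5 Part A: delay named at Grade 4 only | No |

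**3. Resumption after Grade 3 hematologic toxicity.** Dosing falls on Days 1 to 4 and hematology is drawn on Days 1, 8 and 15 (Table 3-3). A low count found on Day 8 or 15 therefore bears on the next Day 1. There Table 10-1 requires hemoglobin of at least 7.0 g/dL (if asymptomatic), neutrophils of at least 1.5 × 10⁹/L and platelets of at least 100 × 10⁹/L. The closing paragraph of 10.5 lets the Investigator reduce a dose by 25% after a delay for a toxicity not otherwise described. Together these cover part of the gap. Other counts in the hematology panel (Table 11-2), such as leukocytes and lymphocytes, have no threshold in Table 10-1, and the closing paragraph of 10.5 deals with dose, not with when to restart.

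**4. Possible size for one Part A stable subject.** Section 8.2.3 names no scan, so the scan at which a site would act is an assumption. Scheduled scans fall at the end of Cycles 2, 4 and 6.

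| Assumed scan | Day (cycles × 28) | Cycles forgone of six | VX-984 doses forgone (3 per cycle) |
|---|---|---|---|
| End of Cycle 2 | 56 | 4 | 12 |
| End of Cycle 4 | 112 | 2 | 6 |
| End of Cycle 6 | 168 | 0 | 0 |

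SAP Section 13 gives PLD duration in weeks as (last dose − first dose + 28)/7. Two cycles give (28 + 28)/7 = 8 weeks, and six give (140 + 28)/7 = 24 weeks. With a full dose D per cycle, dose intensity per 4 weeks is 2D/(8/4) = D and 6D/(24/4) = D. Early stopping thus changes duration, cycles and cumulative dose, but not dose intensity.

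**5. Best overall response.** A worked example in SAP Section 14.1 has stable disease at the first assessment and PR at the second. If 8.2.3 were applied at the first scan, that subject would not reach the on-treatment scan at the end of Cycle 4.

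**6. MTD.** The MTD rests on DLTs in Cycle 1, including the Lead-in Period (SAP Section 15.1). The first scheduled on-treatment scan comes at the end of Cycle 2, and 10.6 applies only after Cycle 1. Neither sentence reaches the DLT data.

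**The case against.** The strongest reply is that the documents already show which text governs stopping. Section 8.2.3 is a rationale section, Sections 9.5 and 10.7 both refer to 8.1.3, and the efficacy text in Section 11 ties disposition to progression. On that view 8.2.3 is a drafting slip that a careful site would pass over. This largely stands, and it limits the severity. It does not remove the conflict: no statement of precedence was found, and the sentence is worded as an instruction.

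The reply on scope also stands. SAP Section 7 says Part B will not be pursued, and the managed-toxicity conflict exists only in Part B.

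A reader might infer more than the documents support:
- *That every stable subject stops at about 8 weeks.* Section 8.2.3 names no scan.
- *That 70% to 90% of subjects are affected*, as the complement of the 10% to 30% response rates in Section 12.1. Those rates are for Part B, and the complement includes subjects who progress and stop under either rule.
- *That stable disease of at least 4 months could never be shown.* On scheduled scans alone it is tight: 56 days plus 4 to 6 weeks is 84 to 98 days, against 4 × 30.4375 = 121.75 days, and the 8-weekly scans in 8.1.4 require six cycles. But the synopsis and Table 3-3 allow Part B subjects without progression CT scans as indicated for up to 1 year, and the endpoint does not require the subject to be on treatment.
- *That 10.6 and 10.5 conflict over Cycle 1.* Section 10.6 requires interruption after Cycle 1 and is silent on Cycle 1.
- *That nothing governs resumption after Grade 3 hematologic toxicity.* Table 10-1 and the end of 10.5 cover part of it.

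**Conclusion.** The concern holds as a conflict of wording. It is more than clerical, because a mandatory sentence followed as written would stop or hold treatment differently from the operative sections. It does not threaten the MTD.

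The number affected cannot be derived, since the documents give no stable-disease rate and no response rate for Part A. For a single stable subject in Part A the difference ranges from none to four of six cycles, depending on the assumed scan. With Part B dropped, the practical effect is mainly on Part A treatment duration, exposure and best overall response. This rests on reading response in the RECIST sense (CR or PR). If 8.2.3 was meant to refer to progression, the correction only makes that explicit.

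**What to change.** Reconcile Section 8.2.3 with 8.1.2.1.4, 8.1.2.2, 8.1.3 and the efficacy text in Section 11. Reconcile Section 10.6 with both parts of 10.5 and its closing paragraph, with a cross-reference to Table 10-1, so that each situation in the table above has one stated rule. The sponsor's clinical team decides which rule holds; this review takes no view. Then check the endpoint and response definitions against the chosen wording.

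The cost is protocol wording, with no change to sample size, data collection or analysis. If no further amendment is planned, the discontinuation reasons listed under SAP Section 10.1, read beside best overall response, would show whether any Part A subject stopped without progression for lack of response. That needs no new output.

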#### 9 STUDY POPULATION

Eligibility will be reviewed and documented by an appropriately qualified member of the Investigator's team before subjects are enrolled.

#### 9.1 Inclusion Criteria

Subjects who meet all of the following inclusion criteria will be eligible.

- 1. Subjects (male and female for Part A and female for Part B) will be at least 18 year of age
- 2. Disease status

#### Part A

Subjects with histologically or cytologically confirmed malignant advanced solid tumors who have progressed on at least 1 prior chemotherapy, and for whom either

- o no standard therapy is available, or
- o PLD at the dose and schedule being used might be considered standard of care

#### Part B

- Subjects with histologically confirmed advanced primary endometrial cancer (locally advanced and incurable endometrial cancer that has been treated with surgery and/or radiation or is ineligible for such treatment), or recurrent or metastatic endometrial cancer, and
- Completed 1 line of chemotherapy treatment with a platinum-containing regimen in the advanced setting
- 3. Measurable disease according to RECIST criteria (Version 1.1)
- 4. WHO performance status of 0 or 1
- 5. Life expectancy of at least 12 weeks

- 6. Hematological and biochemical indices within the ranges shown below at screening. These values must be confirmed within 3 days before the first day of dosing, before study drug administration:
  - a. Hemoglobin:  $\geq 9.0 \text{ g/dL}$
  - b. Absolute neutrophil count:  $\geq 2.5 \times 10^9/L$
  - c. Platelet count:  $\geq 125 \times 10^9/L$
  - d. Serum bilirubin:  $\leq 1.5 \times \text{upper limit of normal (ULN)}$
  - e. ALT, AST:  $\leq 2 \times (ULN)$
  - f. Estimated glomerular filtration rate: ≥ 50 mL/min
  - g. Prothrombin time:  $< 1.25 \times ULN$  unless on anticoagulant therapy and discussed with the medical monitor

In addition, there should not be other clinically significant metabolic or hematologic abnormalities that are uncorrectable or that require ongoing, recurrent pharmacologic management (except subjects who are receiving potassium, magnesium, or other supplementation for an otherwise controlled condition)

- 7. Normal left ventricular ejection fraction on screening assessed by transthoracic echocardiogram or MUGA scan
- 8. Subject will sign and date an informed consent form (ICF)
- 9. Willing and able to comply with scheduled visits, treatment plan, study restrictions, laboratory tests, contraceptive guidelines, and other study procedures.

#### 9.2 Exclusion Criteria

Subjects who meet any of the following exclusion criteria will **not** be eligible.

- 1. Previous radiotherapy (unless brachytherapy), endocrine therapy, chemotherapy, or exposure to investigational medicinal products during the 4 weeks (6 weeks for nitrosoureas and Mitomycin-C) or 4 drug half-lives before the planned administration of the first dose of study drug, whichever is greater. Previous immunotherapy during the 4 weeks before the planned administration of the first dose of study drug
- 2. For Part B only:
  - Subjects with uterine carcinosarcoma
  - o Prior anthracycline therapy
  - o More than 1 prior chemotherapy regimen (a subject who received first-line carboplatin and taxane and then receives the same taxane second-line will be considered to have had 1 prior chemotherapy regimen)
- 3. Unresolved toxicity of CTCAE Grade 2 or greater from previous anti-cancer therapy or radiotherapy, excluding
  - Alopecia

- Anemia or leukopenia if absolute neutrophil counts fall within limits specified in Inclusion Criterion 6 and is not decreasing at the time of treatment
- Other toxicities that in the opinion of the Investigator and the sponsor should not exclude the subject
- 4. History of spinal cord compression or brain metastases, unless asymptomatic, treated, stable, and not requiring treatment with steroids for at least 4 weeks before the planned administration of the first dose of study drug. Any history of leptomeningeal metastases
- 5. Female subjects who are pregnant or lactating at Screening, or plan to become pregnant while on study or within 6 months after the last dose of study drug
- 6. Female subjects of childbearing potential must adhere to contraception guidelines as outlined in the protocol. Female subjects will be considered to be of nonchildbearing potential if they have undergone surgical hysterectomy or bilateral oophorectomy or have been amenorrheic for more than 2 years with a screening serum follicle-stimulating hormone (FSH) level within the laboratory's reference range for postmenopausal females
- 7. Male subjects with partners of childbearing potential must agree to adhere to contraception guidelines
- 8. Male subjects with pregnant or lactating partners or partners who plan to become pregnant while on study or within 6 months after the planned administration of the last dose of study drug
- 9. Major surgery ≤ 4 weeks before first dose of study drug, or incomplete recovery from a prior major surgical procedure
- 10. Cardiac conditions as follows:
  - Clinically significant cardiovascular event within 6 months before Screening:
    - o congestive heart failure
    - o unstable angina pectoris
    - o myocardial infarction
    - Class II/III/IV cardiac disease (New York Heart Association functional classification)
    - o presence of severe valvular heart disease
    - o presence of a ventricular arrhythmia requiring treatment
  - History of arrhythmia that is symptomatic or requires treatment (CTCAE 3), symptomatic or uncontrolled atrial fibrillation despite treatment, or asymptomatic sustained ventricular tachycardia. Subjects with atrial fibrillation controlled by medication are permitted
  - Uncontrolled hypertension (blood pressure  $\geq 160/100$  despite optimal therapy)
  - Second- or third-degree heart block with or without symptoms

- QTc > 450 msec (by either Fridericia's or Bazett's correction) not due to electrolyte abnormality and that does not resolve with correction of electrolytes
- History of congenital long QT syndrome
- History of torsades de pointes (or any concurrent medication with a known risk of inducing torsades de pointes)
- 11. Clinically-significant abnormality, including ejection fraction below normal institutional limits, present on transthoracic echocardiogram performed at Screening
- 12. Prior bone marrow transplant
- 13. Extensive radiotherapy (to greater than 15% of bone marrow)
- 14. Participation or plan of participation in another interventional clinical study while taking part in this study. Participation in an observational study would be acceptable
- 15. Any other condition that in the Investigator's opinion would not make the subject a good candidate for the clinical study, including
  - a. History of human immunodeficiency virus-1 (HIV-1), HIV-2, or unresolved hepatitis B or unresolved hepatitis C infection
  - b. High medical risk because of non-malignant systemic disease including active uncontrolled infection
- 16. Part B: Current active malignancies of other types, with the exception of adequately treated cone-biopsied in situ carcinoma of the cervix uteri and basal or squamous cell carcinoma of the skin. Prior cancer in remission for 2 years or more would not be excluded
- 17. Current therapy:
  - Subjects receiving treatment with medications that are known to be moderate to strong inhibitors or inducers of cytochrome P450 3A4 (CYP3A4) that cannot be discontinued at least 1 week before first dose of study drug and for the duration of the study
  - Subjects receiving treatment with medications that are mainly metabolized by CYP3A4 and have a low therapeutic index that cannot be discontinued at least 1 week before first dose of study drug and for the duration of the study.

